4.6 Follow-up of Serious Adverse Events

Serious AEs that are **identified or ongoing at the last scheduled contact** must be recorded in the data collection tool and reported to the Clinical Safety and Pharmacovigilance department according to the reporting procedures outlined in [Section 4.3](#). This may include **unresolved previously reported SAEs, or new SAEs**. The HCP will follow SAEs until the events are resolved, stabilized, or the patient is lost to follow-up. Resolution means that the patient has returned to the baseline state of health and stabilized means that the HCP does not expect any further improvement or worsening of the patient's condition. The HCP will continue to report any significant follow-up information to Clinical Safety and Pharmacovigilance up to the point the event has been resolved.

4.6.1 Follow-up and Reporting of Serious Adverse Events Occurring after Last Scheduled Contact

Any new SAEs reported by the patient to the HCP that occur **after the last scheduled contact**, and are determined by the HCP to be reasonably associated with the use of Abilify MyCite, should be reported to Otsuka Pharmaceutical Development and Commercialization, Inc (OPDC).

This may include SAEs that are captured on follow-up telephone contact or at any other time point after the defined study period (eg, up to last scheduled contact). The HCP should follow SAEs identified after the last scheduled contact until the events are resolved, stabilized, or the patient is lost to follow-up. The HCP should continue to report any significant follow-up information to OPDC up to the point the event has been resolved or stabilized.

5 Data Collection

5.1 Data Sources

Data sources for this study include demographic and clinical data collected prospectively by study sites, data collected from Abilify MyCite, CCI

CCI [REDACTED] In order to maintain patient confidentiality, each patient will be assigned a unique study-specific patient ID upon study enrollment to use in place of the patient name or any other identifying information (eg, medical record number). Data collected from Abilify MyCite will be transferred to HealthCore and integrated with prospectively collected study data, CCI [REDACTED] will be leveraged for analysis.

For data through the electronic case report forms (eCRFs), the study physician has the ultimate responsibility for the collection and reporting of all clinical and patient data and ensuring that the data are accurate and complete.

5.2 Electronic Case Report Forms and Electronic Data Collection

All clinical study data will be collected at the physician office or over the phone and entered into eCRF by trained site study personnel through a fully validated, 21 Code of Federal Regulations 11 and Health Insurance Portability and Accountability Act (HIPAA)-compliant EDC system.

All study personnel involved in data entry will be trained on patient confidentiality and the EDC system prior to beginning data entry. Site users will be provided eCRF Completion Guidelines to assist with study data collection and entry. Study personnel will access the EDC system through a secure study website.

6 Quality Control and Quality Assurance

6.1 Monitoring

The sponsor has ethical, legal, and scientific obligations to follow this study in an orderly manner in accordance with pragmatic research principles, applicable regulatory requirements, and local laws.

6.2 Auditing/Inspections

This study may be subject to audits or evaluations by regulatory authorities or Otsuka (or its designee). To enable such evaluations and/or audits, the study physician must agree to maintain and allow reasonable access to required patient and study records. The study physician agrees to keep the identity of all participating patients (sufficient information to link records, eg, hospital records), all original signed ICFs, SAE Forms, source documents, detailed records of treatment disposition, and adequate documentation of relevant correspondence (eg, letters, meeting minutes, telephone calls, reports).

Regulatory requirements for the archival of records for this study necessitate that participating physicians maintain detailed clinical data for a period of 3 years after the end of this study.

7 Statistical Methods and Planned Analyses

Complete details of the planned statistical analysis will be presented in the statistical analysis plan (SAP).

7.1 Sample Size

The primary endpoint for the study is the proportion of patients with at least 1 all-cause hospitalization from study start date to Day 180. The assumptions for the sample size calculation were based on input from [REDACTED] for patients diagnosed with SCH, BP1, or MDD who had at least 1 all-cause hospitalization or partial psychiatric hospitalization within the 60 days prior to enrollment. A control group event rate of 36.3% was estimated, weighted based on an expected study distribution of 25% patients with SCH, 25% with BP1, and 50% with MDD. Sample size calculations were based on testing 2 proportions using the Z-test with unpooled variance. The study sample size of 447 patients was calculated based on the following assumptions, informed from [REDACTED] 20% reduction in the proportion of patients with all-cause hospitalizations in the Abilify MyCite group versus the virtual matched control group (29.04% Abilify MyCite versus 36.30% virtual matched control), 1:3 (Abilify MyCite : virtual matched controls) matching, 80% power, and maintaining an overall alpha level of 0.05 with the level of significance in a superiority hypothesis of 0.025. Sample size calculations will be documented in the SAP. Using a 30% dropout rate at 6 months, a sample size of 640 patients will need to be enrolled to ensure completion of 447 patients.

A virtual control group of approximately 1350 patients will be identified from the [REDACTED] and matched to the final sample of Abilify MyCite patients. This will create 3 controls for every 1 Abilify MyCite patient, which reduces the required Abilify MyCite sample size as compared to a 1:1 match while maintaining statistical power. Controls will be matched to Abilify MyCite patients using a propensity score derived from [REDACTED]. This process has been shown to minimize bias associated with sample selection. Further details on the matching process will be included in the SAP.

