7.3.1 Primary Endpoint

The primary endpoint compares the proportion of patients with all-cause hospitalizations between the Abilify MyCite and virtual matched control cohorts. The primary endpoint analysis will be a test of independent proportions. Standard methods for these analysis methods were developed by Fleiss and others¹⁵ and included in all statistical software systems.

These tests are directional in nature since the alternative hypothesis is that the proportions in the Abilify MyCite cohort will be lower than the proportions in the virtual controls.

Adjustments will be made to the alpha level to account for the one-tail nature of the alternative hypothesis (H_A).

- $H_0: P_1 - P_2 \geq 0$ versus $H_A: P_1 - P_2 < 0$

Where:

- P_1 = proportion of Abilify MyCite patients with all-cause hospitalization from study start date to Day 180

- P2 = proportion of virtual control patients with all-cause hospitalization from study start date to Day 180

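### The stated unpooled Z-test and inputs give 422 completing MyCite patients, not 447; 447 gives 82.2% power, so the sample-size statement needs correcting, though the error is conservative

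*Protocol*

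**What the plan says.** Protocol 7.1 (Sample Size) names the method: "Sample size calculations were based on testing 2 proportions using the Z-test with unpooled variance". It then gives the inputs:

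- Control rate: "A control group event rate of 36.3% was estimated".
- Rates compared: "29.04% Abilify MyCite versus 36.30% virtual matched control", a 20% relative reduction.
- Ratio and power: "1:3 (Abilify MyCite : virtual matched controls) matching, 80% power".
- Significance level: "maintaining an overall alpha level of 0.05 with the level of significance in a superiority hypothesis of 0.025".
- Result: "The study sample size of 447 patients was calculated based on the following assumptions".
- Dropout: "Using a 30% dropout rate at 6 months, a sample size of 640 patients will need to be enrolled to ensure completion of 447 patients".

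The control target is about 1,350. Protocol 7.3.1 makes the test one-sided, with MyCite lower under the alternative: "Adjustments will be made to the alpha level to account for the one-tail nature of the alternative hypothesis".

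SAP 4.2 repeats the method, inputs and results. Protocol 7.1 leaves the documentation of the calculation to the SAP, but SAP 4.2 shows no formula. Neither document mentions a continuity correction, a pooled variance or a safety margin added to the calculated figure.

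**The concern.** The number, the method and the power are presented as one calculation, and every input that the formula needs is legible. The blacked-out text in these sections stands where the source of the assumptions is named, not where the rates, ratio, power, significance level or method are given. A reader should therefore be able to reproduce 447, and cannot.

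The figure matters because 447 leads to the enrolment target of 640 and the control target of about 1,350. It also matters because SAP 4.2 allows the ratio to fall to 1:2 and then 1:1 if controls are scarce. Reworking power for a changed ratio needs a formula and an arm order that reproduce the starting figure.

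**Working it through.** **Inputs** (Protocol 7.1, repeated in SAP 4.2): p1 = 0.2904 (MyCite), p2 = 0.3630 (control), difference 0.0726, k = 3 controls per MyCite patient, one-sided significance level 0.025 (z = 1.960), power 80% (z = 0.842). The squared sum of the z values, before rounding, is 7.849.

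**1. The stated method.** For the MyCite arm,

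n1 = (1.960 + 0.842)² × [p1(1 − p1) + p2(1 − p2)/k] / (p1 − p2)²

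- p1(1 − p1) = 0.2904 × 0.7096 = 0.20607
- p2(1 − p2)/3 = 0.3630 × 0.6370 / 3 = 0.07708
- sum = 0.28314
- n1 = 7.849 × 0.28314 / 0.0726² = 2.2224 / 0.0052708 = 421.6, so **422**

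The plan's 447 is not reproduced. The gap is 447 − 422 = 25 patients, or 25/422 = 5.9%.

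**2. Power at 447 with 3 × 447 = 1,341 controls.**

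- Standard error = √(0.28314/447) = 0.02517
- 0.0726/0.02517 − 1.960 = 0.925, which corresponds to **82.2%** power

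**3. Dropout does not explain the gap.** The figure 447 is stated before dropout, and 447/0.70 = 638.6, so 639, which agrees with the stated 640. The same step from 422 gives 422/0.70 = 602.9, so 603 enrolled, and 3 × 422 = 1,266 controls.

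**4. Can another reading give 447?**

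| Variant | MyCite patients |
|---|---|
| Unpooled, as stated | 422 (421.6) |
| Unpooled, one-sided 0.05 | 333 (332.1) |
| Unpooled, two-sided 0.025 | 511 (510.6) |
| Unpooled with continuity correction | 440 (439.8) |
| Pooled variance under the null only | 441 (440.4) |
| Pooled variance under the null only, with continuity correction | 459 (458.6) |
| Pooled variance throughout, weighted 1:3 | 449 (448.6) |
| Arcsine | 436 (435.5) |
| Unpooled, 1:3 ratio reversed | **447 (446.6)** |

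Exact binomial enumeration in place of the normal formula needs about 427 for the plain unpooled test and 446 for the unpooled test with continuity correction. Neither is 447.

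**5. The reversed ratio in full.** If the 36.30% arm is the smaller arm,

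n = 7.849 × [0.3630 × 0.6370 + 0.2904 × 0.7096/3] / 0.0726² = 7.849 × (0.23123 + 0.06869) / 0.0052708 = 446.6, so 447.

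This keeps the named method, rates, power and significance level and changes only which arm is tripled. It describes 447 controls and 1,341 MyCite patients, the opposite of the design.

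**The case against.** The strongest reply is that nothing harmful follows. The figure 447 exceeds 422, so the 80% target is met with a little to spare, and no design quantity has to change. This stands. A reader might infer that the study is underpowered or mis-sized in a harmful direction; under the stated assumptions the opposite is true.

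A second reply is that the documents do not say whether a continuity correction was applied. With one, the unpooled test at 447 has about 80.7% power, close to the stated 80%. This shows that 447 is not far off and that 82.2% assumes no correction. It does not rescue the statement: the corrected formula gives 440, and an unstated correction would itself need reporting.

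A third reply is that the variance formula may be correctly named and only the arm order wrong. That is plausible, and it is why pointing to pooled variance alone would mislead: neither pooled form gives 447. A reader might go further and take transposed arms as established. The exact match is suggestive, but the documents show no working, so it cannot be proved.

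A fourth reply is that the Z-test is not the SAP's primary analysis. SAP 4.4 names a McNemar paired test, while Protocol 7.3.1 names a test of independent proportions. This also stands. Neither 80% nor 82.2% is the power of the McNemar test, and a corrected sentence must not suggest otherwise.

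Finally, SAP 5.0 records that the study ended after two patients with no efficacy assessment, so no inference will rest on 447. That lowers the urgency but does not make the statement correct.

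**Conclusion.** The point holds as an error in the sample-size statement. The named test with the stated inputs requires 422 completing MyCite patients, not 447, and 447 gives 82.2% power, not 80%. The differences are 25 patients (5.9%) and 2.2 percentage points, both on the safe side.

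This rests on the stated rates, the 1:3 ratio, a one-sided level of 0.025, no continuity correction and independent groups. It also rests on 1:3 actually being achieved. With 447 MyCite patients, the same formula gives about 77% power at SAP 4.2's fallback of 1:2 (standard error √[(0.20607 + 0.23123/2)/447] = 0.02683) and about 64% at 1:1 (standard error √[(0.20607 + 0.23123)/447] = 0.03128).

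A reader might also infer that enrolment should be cut to 603. The documents give no reason to do so: the 37 extra enrolments (640 − 603) are harmless to the inference, and the fault lies in the description.

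**What to change.** In Protocol 7.1 and SAP 4.2:

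1. Check the arm order in the original calculation.
2. Then either restate the figure as *447 completing MyCite patients give about 82% power with the unpooled Z-test at 1:3 (80% needs 422)*, or state the formula, arm order and any correction that actually give 447. Replacing unpooled with pooled is not enough, because the result is 441 (or 449 if pooled throughout).
3. Add that this power is for the independent-proportions Z-test and does not carry over to the McNemar test named in SAP 4.4.

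The cost is a sentence or two in each document. Enrolment can stay at 640 and the control target at about 1,350. As the study has stopped, the benefit is an accurate record and a calculation that can safely be reused.

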7.2 Analysis of Demographic and Baseline Characteristics

Demographic and baseline characteristics will be summarized for the study population overall and by treatment (Abilify MyCite versus virtual matched controls). Discrete

variables will be reported as count (frequency) and percent for each category. Continuous level variables (interval, ratio) will be reported as mean and standard deviation. Where applicable, range, minimum, maximum, and median will also be reported. Other statistics, measures of central tendency, and measures of dispersion may also be reported as outlined in the SAP.

It is likely that the virtual matched controls will lack some variables that are available to the Abilify MyCite sample. As a result, a comprehensive list of each variable in the Abilify MyCite sample will be listed, while "N/A" will be listed for each variable that is not available in the virtual matched control cohort. Balance in baseline characteristics across the 2 cohorts will be evaluated prior to analysis.

The details of this analysis will be fully described in the SAP.

7.3 Effectiveness Analyses

Effectiveness analysis for this study refers to the difference in the study endpoints within the Abilify MyCite cohort and the virtual matched controls. This analysis is further outlined in the primary endpoint and secondary endpoints sections ([Section 7.3.1](#) and [Section 7.3.2](#)). A summary table will be presented reporting the difference between cohorts at Day 180. Potential adjustment for baseline values or differences that exist in the samples will be further outlined in the SAP.

7.3.1 Primary Endpoint

The primary endpoint compares the proportion of patients with all-cause hospitalizations between the Abilify MyCite and virtual matched control cohorts. The primary endpoint analysis will be a test of independent proportions. Standard methods for these analysis methods were developed by Fleiss and others¹⁵ and included in all statistical software systems.

These tests are directional in nature since the alternative hypothesis is that the proportions in the Abilify MyCite cohort will be lower than the proportions in the virtual controls.

Adjustments will be made to the alpha level to account for the one-tail nature of the alternative hypothesis (H_A).

- $H_0: P_1 - P_2 \geq 0$ versus $H_A: P_1 - P_2 < 0$

Where:

- P_1 = proportion of Abilify MyCite patients with all-cause hospitalization from study start date to Day 180

- P2 = proportion of virtual control patients with all-cause hospitalization from study start date to Day 180

7.3.2 Secondary Endpoint

The secondary endpoint compares the difference between groups (Abilify MyCite versus virtual matched controls) in the proportion of patients with at least 80% PDC (with antipsychotic medication) from baseline to Day 180.

This analysis will be a test of independent proportions between the Abilify MyCite and virtual matched control groups.

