- ≥ 180 days of medical and pharmacy enrollment following index date

Prior to matching, the pool of potential controls and the Abilify MyCite cohort will be stratified by psychiatric diagnosis (SCH, BP1, MDD). The Abilify MyCite cohort psychiatric diagnosis will be based on the psychiatric diagnosis recorded in the eCRF. The potential controls psychiatric diagnosis will be based on the psychiatric diagnosis identified [REDACTED] CCI. In the event that more than one of the qualifying psychiatric diagnoses is identified [REDACTED] CCI, the following hierarchy will be applied to potential controls: SCH>BP1>MDD.

From this pool of patients, combined with the active arm, logistic regression will be used within each psychiatric diagnosis to estimate a propensity score for each patient, where propensity refers to a patient's pre-index likelihood to be in the active arm. The dependent variable equals 1 for patients in the active arm and 0 for the controls. The following variables may be considered for inclusion in the propensity score model; a final determination will be made using descriptive study results on patient baseline characteristics.

- Age
- Gender
- Month of index date
- Plan type (commercial, Medicaid, or Medicare health plan with medical and pharmacy benefits)
- Number of fills for any atypical antipsychotic over 6-12 months prior to index date
- [REDACTED] CCI
- Occurrence/number of visits with a psychiatrist over 6-12 months prior to index date
- Comorbidities over 6-12 months prior to index date

¹⁶ Defined as a medical claim with place of service code = 52 ("Psychiatric Hospitalization"), or with HCPCS codes H0035 or S0201.

- Region of patient residence (Northeast, South, Midwest, West)

The estimated propensity scores will be used to match active arm patients to the virtual controls in a 1:3 ratio. Prior to assessing outcomes, the validity of the propensity score adjustment will be assessed by (1) graphically examining the overlap in propensity scores across treatment and control groups¹⁷, and (2) comparing balance in all baseline characteristics across the cohorts via standardized mean differences. A standardized mean difference >10% in absolute value will be used to indicate potential imbalance that may warrant further investigation or adjustment (e.g. through regression analysis).¹⁸ Propensity score models will be finalized prior to the assessment of outcomes.

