4.4 Primary Endpoint

The primary endpoint is the difference in the proportion of patients with at least 1 all-cause hospitalization for the Abilify MyCite versus virtual matched control cohorts from baseline to Day 180. The primary endpoint analysis will be a McNemar's paired sample chi-square test between the treatment cohorts.

This test is directional in nature as it is testing the alternative hypothesis (H_A) that the proportion patients hospitalized will be lower in the Abilify MyCite cohort than the virtual control cohort. Adjustments will be made to the alpha level to account for the one-tail nature of the alternative hypothesis.

- $H_0: P_1 - P_2 \geq 0$ versus $H_A: P_1 - P_2 < 0$

Where:

- P_1 = proportion of Abilify MyCite patients with all-cause hospitalization from baseline to Day 180
- P_2 = proportion of virtual control patients with all-cause hospitalization from baseline to Day 180

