4.5 Secondary Endpoint

The secondary endpoint compares the difference between groups (Abilify MyCite versus virtual matched controls) in the proportion of patients with at least 80% PDC (with antipsychotic medication) from baseline to Day 180.

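### The only test stated for the PDC endpoint treats 1:3 matched cohorts as independent samples, and the SAP names no test to replace it; if PDC is positively correlated within matched sets, the result is modestly conservative

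*Protocol*

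**What the plan says.** - **Secondary test, protocol.** Section 7.3.2: "This analysis will be a test of independent proportions between the Abilify MyCite and virtual matched control groups".
- **Secondary test, SAP.** Section 4.5 defines the comparison, "The secondary endpoint compares the difference between groups (Abilify MyCite versus virtual matched controls) in the proportion of patients with at least 80% PDC", and stops there. It gives no test, variance method, alpha or sidedness.
- **Matching.** SAP 3.4 splits both cohorts by diagnosis and fits a propensity model within each diagnosis. Then: "The estimated propensity scores will be used to match active arm patients to the virtual controls in a 1:3 ratio". One variable that may enter the model is "Number of fills for any atypical antipsychotic over 6-12 months prior to index date". SAP 4.2 allows the ratio to fall to 1:2 and then 1:1.
- **Primary test.** Protocol 7.3.1 says "The primary endpoint analysis will be a test of independent proportions". SAP 4.4 changes this: "The primary endpoint analysis will be a McNemar's paired sample chi-square test between the treatment cohorts".
- **Division of labour.** The opening of Protocol Section 7 leaves the full analysis detail to the SAP.
- **Error level.** The 0.025 superiority level (Protocol 7.1, SAP 4.2) and the one-tailed hypothesis (Protocol 7.3.1, SAP 4.4) are given for the primary endpoint. SAP 4.1 sets 5% for inferential tests in general.

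**The concern.** A test for two independent samples takes the covariance between a treated patient and that patient's controls to be zero. Matching within diagnosis on a score that may include earlier antipsychotic fills could make PDC status alike within a set. In that case the usual standard error is larger than the true one, the interval is too wide, and some power is lost on the trial's only secondary endpoint.

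The two documents also leave an inconsistency that needs no assumption about correlation. Read together, they treat the same matched cohorts as paired for hospitalization and as independent for PDC, and nothing explains the difference.

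**Working it through.** **1. The plan's own figure.** No sample size or power is given for PDC. The only sizing is for the primary endpoint: 447 completers at 1:3, 29.04% versus 36.30%, 80% power, level 0.025.

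- Two independent proportions, pooled variance under the null: 441 (1.3% below 447).
- The unpooled form that the text names: 422 (5.6% below).
- Power at 447 versus 1,341 (3 × 447): 80.6% pooled, 82.2% unpooled.

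These are independent-samples formulas, so the sizing counts on no gain from correlation within sets.

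**2. What three controls per patient buy.** With n treated patients and k controls each, the independent-samples variance is p(1−p)(1+1/k)/n. Moving from 1:1 to 1:3 multiplies the standard error by √[(4/3)/2] = √(2/3) = 0.816. For the primary endpoint the pooled requirement falls from 654 to 441. An independent-samples test keeps all of this.

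**3. What ignoring the sets costs.** Take equal rates and an exchangeable correlation r within each 1:3 set, with s² = p(1−p):

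Var(treated − mean of 3 controls) = s²[1 + (1+2r)/3 − 2r] = (4/3)s²(1−r).

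The independent-samples test uses (4/3)s². Its standard error is therefore 1/√(1−r) times the true one, whatever the PDC rate. The same factor holds at 1:2 and 1:1.

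**4. Numbers.** Inputs: 447 sets (from the plan); PDC rate 50%, r, and one-sided 0.025 (all assumed for PDC). The independent-samples SE is √(0.25 × (4/3)/447) = 2.73 points. The difference detectable with 80% power is (1.960 + 0.842) × 2.73 = 7.65 points. The last column gives power at that 7.65-point difference.

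| r | Independent SE too large by | Matched SE (points) | Detectable, matched (points) | Actual one-sided error, independent test | Power, independent vs matched |
|---|---|---|---|---|---|
| 0 | 0% | 2.73 | 7.65 | 2.5% | 80.0% vs 80.0% |
| 0.05 | 2.6% | 2.66 | 7.46 | 2.2% | 80.6% vs 82.0% |
| 0.10 | 5.4% | 2.59 | 7.26 | 1.9% | 81.3% vs 84.0% |
| 0.20 | 11.8% | 2.44 | 6.84 | 1.4% | 82.7% vs 88.0% |

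If r were −0.05, the direction would reverse: matched SE 2.80 points, actual one-sided error 2.8%.

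**5. Which r is plausible.** The documents give none. Stratification by diagnosis is the one certain source. With the planned mix of 25/25/50% (SCH/BP1/MDD), r from diagnosis alone is the between-diagnosis variance divided by m(1−m), where m is the overall rate:

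- Assumed PDC rates 40/50/60%: m = 0.525, r = 0.006875/0.249375 = 0.028, SE 1.4% too large.
- Assumed PDC rates 30/50/70%: m = 0.55, r = 0.0275/0.2475 = 0.11, SE about 6% too large.

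Prior fills could add to this, but they are only a candidate variable. Patients are matched on a composite score, so equal scores do not imply equal fill counts. The r = 0.20 row is an outer illustration without support in the documents.

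**The case against.** The strongest reply is that this is a gap in the SAP more than a wrong choice of test. The protocol is consistent with itself, using independent samples for both endpoints. The SAP replaced that test for the primary endpoint, so 7.3.2 may not be the final intent for PDC either. This stands in part. Intent cannot be read from silence, but 7.3.2 remains the only PDC test stated anywhere, and an analyst following the text would use it.

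A reader might infer three stronger things that the documents do not support:

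- **That the standard error is certainly too large.** This needs r above zero, which is plausible but not given.
- **That the precision gained by matching is lost.** The efficiency the documents claim comes from three controls per patient, and step 2 shows that it is kept. The propensity score itself is justified in Protocol 7.1 as reducing selection bias, which the choice of test does not affect.
- **That false-positive risk rises.** With positive r the error goes the other way.

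It is also fair that one-sided 0.025 is borrowed from the primary endpoint, so the error and power figures above are illustrative. Finally, SAP 5.0 records that the study stopped after two subjects with only baseline data summarized, so no PDC comparison will be run under this SAP.

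**Conclusion.** The point holds as a minor flaw in the written plan. The one stated PDC test ignores the matched sets, and the SAP neither confirms nor replaces it, although it treats the primary endpoint as matched. That part rests on the text alone.

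The size rests on an assumed, exchangeable within-set correlation: no effect at r = 0, and a standard error about 1% to 5% too large for r between roughly 0.03 and 0.10. At a difference giving 80% power under r = 0, the power forgone is 1.4 points at r = 0.05 (82.0 − 80.6) and 2.7 points at r = 0.10 (84.0 − 81.3). The error is conservative when r is positive. The unstated alpha and sidedness for PDC are part of the same gap. The early stop removes any effect on this study's results; the point matters for the record and for reuse of the design.

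**What to change.** In SAP 4.5, state that the PDC endpoint is analysed as a difference in proportions with its confidence interval, with variance clustered on matched set, at a named alpha and sidedness. This keeps the stated estimand, works at 1:3, 1:2 or 1:1, and gives suitable error bars whatever the sign of r. A Mantel-Haenszel test stratified by matched set can be added as support. Align Protocol 7.3.2 with it.

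Two substitutes should be avoided. The standard McNemar test named in SAP 4.4 is for 1:1 pairs and does not handle 1:3 sets. Conditional logistic regression would replace the stated difference in proportions with a conditional odds ratio, and it discards sets in which all members have the same outcome.

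The cost is one SAP sentence, matching wording in the protocol, a matched-set identifier kept in the analysis dataset, and a line of code. No extra patients or data are needed.
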